 - b. Minor subjects and their parents or guardians will be informed that we will be doing urine drug screens as part of the routine study evaluations. We will explicitly inform parents and potential minor subjects, in the written informed consent document and orally, that we will not inform the parent of the results of the drug test, because revealing this information could affect the willingness of the minor subject to participate in the study or answer truthfully. We will tell both the minor subject and the parent or guardian our clinical policy regarding confidentiality, as follows: If a minor subject is found to have a positive drug screen, the PI will discuss the risks of drug use with the subject, and encourage the minor subject to discuss their use of drugs with their parent or guardian. If the subject is found to have a substance use disorder, we will discuss the need for treatment with the subject, and encourage the subject to allow us to speak with their parent or guardian about our concerns.
 - c. Participants who are minors will be informed that their parent will be notified in the event that they are engaging in or plan to engage in behavior (i.e., suicidal attempt) that is dangerous to themselves or others.
 - d. To summarize, our procedures will follow routine clinical research procedures to reduce risk to participants, and follow all State regulations regarding treatment of minors and informing parents and guardians. A single clinician will attempt to engage the minor in a therapeutic relationship, and maintain confidentiality unless there is a specific, immediate safety risk (e.g., suicidal ideation).

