Data and Safety Monitoring Plan: All studies conducted at this site are reviewed and approved by an Institutional Review Board (IRB). A signed informed consent, assent (as applicable), and HIPAA Authorization form is obtained from the subject or the subject's legally authorized representative prior to the initiation of any study related procedures. Handling, dispensing and administration of the investigational drug must be in accordance with all state and federal laws and regulations. The IRB requires regular updates on the status of research projects, including the number of participants enrolled, adverse events or unanticipated problems, number of withdrawals from the project, complaints about the research, and any protocol changes. Any significant adverse events (which will be reported to the IRB as soon as possible, never to exceed 10 days from when the adverse event becomes known to the PI or study staff). The IRB also monitors the consent forms and ensures that appropriate HIPAA information is included.

Adverse events in this research project are expected to be uncommon. However, should we find that a participant has an adverse event we will take the appropriate steps to deal with the issue. Staff will consult with the study physician and the PI and address patient safety. Any possible serious adverse events will be reported to the PI immediately. In addition, the PI will conduct a safety review at a weekly frequency. All subjects will be reviewed at a regularly scheduled weekly meeting and any adverse events will be discussed. Adverse events will be defined as any adverse occurrence between the signing of consent and 2 weeks after the end of study.

participation. Unanticipated risks are those risks not cited in the protocol or known risks of the illness under study. Unanticipated risks include instances where anticipated risks exceed expectations in terms of their magnitude or frequency.

The Principal Investigator will attribute adverse events as follows:

- Definite: Adverse event(s) will clearly be related to investigational agent(s) or other intervention
- Probable: Adverse event(s) will likely be related to investigational agent(s)
- Possible: Adverse event(s) may be related to investigational agent(s)
- Unlikely: Adverse event(s) will doubtfully be related to investigational agent(s)
- Unrelated: Adverse event(s) will clearly not be related to the investigational agents(s)

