A serious AE will be one that results in death or the immediate risk of death, hospitalization or the prolonging of an existing hospitalization, persistent or significant disability/incapacity or a congenital anomaly/birth defect. Adverse events will be graded as follows:

- No adverse event or within normal limits
- Mild adverse event
- Moderate adverse event
- Severe adverse event resulting in hospitalization or prolongation of existing hospitalization, a persistent or significant disability/incapacity, or a congenital anomaly/birth defect.
- Life-threatening or disabling adverse event
- Fatal adverse event

The principal investigator will evaluate the adverse event and determine whether the adverse event affects the Risk/Benefit ratio of the study, whether the blind should be broken, and whether modifications to the protocol (at Risks to Subjects, or in Procedures) or consent form (at Risks and Inconveniences) are required. Serious unanticipated adverse events will be reported within 24 hours to the local IRB, the FDA, and NIMH if unblinded on treatment course (vs. placebo), unless the attribution is that the adverse event is unrelated to study participation. Either the principal investigator or the RCP have the authority to stop or suspend the study. A summary of the adverse events will be reported to the RCP when reapproval of the protocol is sought. The summary will include number of subjects enrolled and a summary of graded adverse events to date.

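### The serious-event definition is a closed list with no category for medically important events, so a suicide attempt managed without admission can be classed as non-serious and its immediate report to the PI is not assured

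*Combined protocol and SAP*

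**What the plan says.** All the safety text is in the Human Subjects part of the protocol. Under Data and Safety Monitoring Plan, the definition reads "A serious AE will be one that results in death or the immediate risk of death, hospitalization or the prolonging of an existing hospitalization", and the list closes with "persistent or significant disability/incapacity or a congenital anomaly/birth defect". Nothing there or elsewhere marks these outcomes as examples or adds a judgement clause.

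The severity scale that follows uses the same outcomes. Its third adverse-event grade begins "Severe adverse event resulting in hospitalization or prolongation of existing hospitalization" and goes on to disability and birth defect.

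Two reporting routes depend on the word *serious*:

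- "Any possible serious adverse events will be reported to the PI immediately"
- "Serious unanticipated adverse events will be reported within 24 hours to the local IRB, the FDA, and NIMH", subject to further conditions on unblinding and attribution.

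Other routes do not depend on it. When a participant has an adverse event, "Staff will consult with the study physician and the PI and address patient safety"; in addition, "the PI will conduct a safety review at a weekly frequency". Significant adverse events go to the IRB within 10 days at most, but *significant* is not defined.

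Under Protections Against Risk, item 7c, the parents of minors are told of "behavior (i.e., suicidal attempt) that is dangerous to themselves or others". Active suicidal ideation is also an exclusion criterion at entry.

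**The concern.** The trial enrols people aged 12 to 30 at clinical risk of psychosis, and the protocol itself foresees suicidal behaviour. It screens for suicidal ideation at entry and treats an attempt as grounds for overriding a minor's confidentiality. Yet no text links an attempt after enrolment to the serious-event definition. Because the definition looks only at what the event resulted in, classification can turn on whether the participant was admitted.

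The same gap applies to any other event in which prompt treatment averted a listed outcome. At stake are how quickly the PI is certain to hear of such an event and whether eight sites would classify the same event in the same way.

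**Working it through.** No arithmetic applies. The plan states no figure on this point and gives no event rate. The check applies the written rule to one case: a suicide attempt treated without admission, not judged an immediate risk of death, and leaving no lasting disability.

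**Step 1: the seriousness criteria.**

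| Criterion in the definition | Met? |
|---|---|
| Death, or immediate risk of it | No, by the description of the case |
| Admission, or a longer existing stay | No, not admitted |
| Lasting or significant disability | No |
| Birth defect | Not applicable |
| Any other medically important event | No such criterion exists |

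The event is therefore non-serious under the stated rule. Had it been judged an immediate risk of death, it would qualify. The claim is that such an attempt *can* be classed as non-serious, not that every attempt would be.

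**Step 2: the severity grades.** The severe grade needs admission, disability or a birth defect, and the two grades above it need a threat to life, disablement or death. The case therefore reaches moderate at most, so the severity scale does not make up for the gap.

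**Step 3: the reporting routes.**

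| Route | Depends on *serious*? | Applies to this case? |
|---|---|---|
| Immediate report to the PI | Yes (possible serious events) | Not assured |
| 24-hour report to IRB, FDA and NIMH | Yes, and also on *unanticipated*, unblinding and attribution | Normally no, even if the event were serious |
| Staff consultation with the physician and PI | No | Yes, with no time limit stated |
| Weekly PI safety review and weekly meeting | No | Yes |
| IRB report within 10 days | No, depends on *significant* | Possibly; the term is undefined |
| DSMB review three times a year | No | Yes, as part of overall safety review |

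**Step 4: why the 24-hour route is normally out of reach.** On its natural reading, the plan's definition of unanticipated risks leaves out risks that the protocol already cites and known risks of the illness, unless they exceed expectation in size or frequency. Suicidality is cited in the exclusion criteria and in Protections Against Risk. An attempt would therefore usually count as anticipated, whatever its seriousness.

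**Step 5: what changes.** For this case, non-serious classification removes the certainty of an immediate report to the PI. Consultation without a time limit and a weekly review remain.

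**The case against.** The strongest reply is that little is lost in practice. The immediate-report sentence covers *possible* serious events. When staff first hear of an attempt, its lethality and the need for admission may be unsettled, so a careful site would report at once. The PI is consulted on any adverse event, reviews safety weekly, and evaluates adverse events for risk and benefit whether or not they are serious. This stands, and it limits the point to immediacy and classification. It does not remove the point: *possible* still refers back to the closed list, so once it is clear that no listed outcome occurred, nothing requires an immediate report.

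Item 7c, it may also be said, is a confidentiality rule for minors and classifies no adverse events. That is right. A reader might infer that the two sections contradict each other, but they do not. Item 7c shows only that the protocol regards an attempt as dangerous while the safety definition need not capture it.

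A reader might also infer that such attempts escape the 24-hour report because they are non-serious. The documents do not support that as a general consequence, because that route also requires the event to be unanticipated and to meet the other conditions.

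Finally, a medically-important-event criterion is something the reviewer adds; no text in the protocol demands it. That is fair, and the point is a recommended improvement to a design choice, not a breach of the protocol's own rule.

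**Conclusion.** The point holds in a limited form. The definition is closed, and a suicide attempt without admission, immediate risk of death or lasting disability is non-serious under it. What is lost is guaranteed immediate notice to the PI and uniform serious classification across eight sites. The PI's eventual awareness is not lost.

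Three assumptions support this: the list is read as exhaustive, as its wording indicates; *possible serious* is read as possibly meeting that list; and *unanticipated* is read in its natural sense.

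No number of affected events can be given, since the documents supply neither a rate of self-harm nor a share admitted. A reader might infer that serious-event totals for the safety and tolerability aim would be understated. The statistical section specifies no such total, and the one tabulation described is a summary of graded adverse events, in which the attempt would still appear. The point rests on the wording of the definition and is of modest weight.

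**What to change.** In the Data and Safety Monitoring Plan, add one criterion to the serious-event definition: other medically important events that, in the PI's judgement, endangered the participant or needed intervention to prevent one of the listed outcomes, expressly including any suicide attempt. State that the immediate-report sentence uses this same definition, keeping *possible* so that staff report before the PI has judged the event. Naming suicide attempts means that sites need make no judgement for that case.

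This alters classification and reporting only; it changes no treatment or clinical procedure. It would not normally bring suicide attempts into the 24-hour report, whose other conditions stay as they are. The cost is a sentence in the plan, a matching entry on the adverse-event form, and a few more serious-event reports for sites to file.

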NAPLS OMEGA 3 STUDY PROTOCOL

VERSION 2-28-17

Randomized Double-Blind Trial
of Omega-3 Fatty Acid
versus Placebo in Patients
at Risk for Psychosis

“THE OMEGA-3 STUDY”

[name]., Principal Investigator
University of California, Los Angeles

[name]., Co-Principal Investigator, and [name].
University of California, San Diego

[name]., and [name].
Yale University

[name].
University of Calgary

[name].
North Shore-Long Island Jewish Health System

[name].
Emory University

[name].
Harvard University/Massachusetts Mental Health Center

[name]., MPH
University of North Carolina, Chapel Hill

Proposal to the National Institute of Mental Health
As a Supplement to NIMH 1R01MH081902-01A1
“Predictors and Mechanisms of Conversion to Psychosis”

Statement of Purpose

The overall goal of the present study is to determine whether Omega-3 Fatty Acids potentially prevent onset of psychosis and improve clinical symptoms and functional outcome in youth at elevated clinical risk for schizophrenia and related disorders. The specific aims are: (1) To determine whether the rate of progression to psychosis is lower at 12-month follow-up among patients randomly assigned to six months of treatment with Omega-3 Fatty Acids compared to those randomly assigned to six months of treatment with placebo, (2) To determine whether Omega-3 Fatty Acids are more efficacious than placebo for prodromal symptoms, negative symptoms, and functioning, (3) To assess the safety and tolerability of Omega-3 Fatty Acids in this population, and (4) To conduct analyses of neuroimaging, neurocognitive, electrophysiological and other ancillary data to explore mechanistic explanations for the hypothesized benefits of Omega-3 Fatty Acids on clinical and functional outcomes (e.g., increases in white matter integrity and processing speed).

Background

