For evaluation of the primary outcome measure (time to conversion), we will use Cox's proportional hazards model and Kaplan-Meier survival analysis as implemented in SAS PROC PHREG and LIFETEST. The secondary and tertiary outcome variables, all treated as continuous variables, will be examined as a function of treatment condition and site using mixed effects regression models. Mixed effects models permit the estimation of symptom trajectories at the level of the individual participant over time. Then the random coefficients from these within-participant trajectories are modeled as a function of treatment condition and appropriate baseline covariates (e.g., initial severity of symptoms; age or gender). At the level of the individual participant, time-varying covariates (e.g., antipsychotic treatment or not) can also be controlled, thus permitting the estimation of within-participant trajectories over and above any time-varying covariates. Similar approaches will be used to examine the trajectory of functional outcome scores. The advantages of mixed effects models over traditional repeated measures models are that they allow for (1) the inclusion of participants with missing data, (2) observations that are unequally spread out over time (both within and between participants), and (3) more flexible modeling of variance and covariance patterns of residuals. We will use two programs – SAS PROC MIXED and MIXREG – to examine these models.

Human Subjects

Only participants who meet eligibility criteria for and have previously been consented for the North American Prodrome Longitudinal Study (NAPLS) will be invited to participate. Participants will thus include individuals who are referred or respond to announcements because they may be experiencing symptoms that are associated with the prodrome of psychosis. These individuals will be referred by community health care providers or will be self-referred in response to media announcements or internet searches. Recruitment involves providing announcements to local primary care practitioners, including community pediatricians, family practice physicians, local clergy, educators, clinical social workers, psychologists, and psychiatrists. This information will include a letter introducing the study, and a brochure that describes prodromal symptoms.

Based on enrollment in NAPLS to date, about 65% of the sample are expected to be males. About 20% of subjects are expected to be African American and about 10% Latino.

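### The adverse-event scale defines Severe by seriousness outcomes and places disability in two grades, so graded summaries cannot separate intense non-serious events from moderate ones

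*Combined protocol and SAP*

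**What the plan says.** The Data and Safety Monitoring Plan (under Human Subjects) first defines seriousness: "A serious AE will be one that results in death or the immediate risk of death, hospitalization or the prolonging of an existing hospitalization", continuing with "persistent or significant disability/incapacity or a congenital anomaly/birth defect".

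A six-step grading list follows directly: none, mild, moderate, severe, life-threatening or disabling, fatal. Mild and moderate are bare labels; the entry for the latter reads in full "Moderate adverse event". The next step is worded "Severe adverse event resulting in hospitalization or prolongation of existing hospitalization, a persistent or significant disability/incapacity, or a congenital anomaly/birth defect", and the one above it "Life-threatening or disabling adverse event".

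The grades have one stated use. When reapproval of the protocol is sought, a report goes to the body the protocol calls the RCP: "The summary will include number of subjects enrolled and a summary of graded adverse events to date". The same paragraph gives the RCP, like the principal investigator, authority to stop or suspend the study.

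The third specific aim in the Statement of Purpose is "To assess the safety and tolerability of Omega-3 Fatty Acids in this population".

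**The concern.** Severity and seriousness are different properties of an adverse event. Severity is how intense it is; seriousness is whether it led to one of a fixed list of outcomes. An event can be intense without being serious, and a grading scale is the usual place to record that. Here the grade that should carry intensity is worded as a list of serious outcomes.

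This matters because of the product. Potential Risks, item 6, names aftertaste and dose-dependent gastrointestinal disturbance as possible side effects. Such effects would usually not meet a seriousness criterion, so intensity is the property on which they would mainly differ. Protections Against Risk, item 4, expects that some may become burdensome enough for a participant to take fewer capsules or stop. Under the stated rule, such an event shares a grade with one that is merely moderate.

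The Data and Safety Monitoring Plan also treats an anticipated risk as unanticipated when it is larger or more frequent than expected. Judging whether a non-serious effect is larger than expected needs an intensity scale, and the list offers only two undefined labels for it.

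The double placement of disability is a second problem. Eight sites grade events, and nothing tells them which of the two grades to choose.

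**Working it through.** No arithmetic on rates, power or sample size applies, and the plan states no figure to reproduce. The check sets the two definitions side by side and then looks for every planned use of the grades.

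**Step 1. Map each seriousness criterion to a grade.** The serious-event definition has four criteria. The first has two parts, shown on separate rows.

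| Seriousness criterion | Grade(s) that contain it |
|---|---|
| Death | Fatal |
| Immediate risk of death | Life-threatening or disabling |
| Hospital admission or a longer stay | Severe |
| Lasting or significant disability | Severe; also Life-threatening or disabling |
| Congenital anomaly | Severe |

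Three of the four criteria sit in Severe, almost word for word. The remaining one is split across the two grades above it.

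**Step 2. Count the grades open to an intense, non-serious event.** Six steps less the one for no event leaves 6 − 1 = 5 grades. Three of them (severe, life-threatening or disabling, fatal) are tied to outcomes, leaving 5 − 3 = 2: mild and moderate. Neither is defined, and no other section of the protocol supplies an intensity scale.

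**Step 3. Test the wording for another reading.** The Severe entry could mean any event with a listed outcome, or an intense event that also has a listed outcome. Both readings shut out an intense event with no listed outcome, so the conclusion does not depend on the choice.

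**Step 4. Check that the grades are mutually exclusive.** An event that leaves lasting disability satisfies the Severe entry by name and also satisfies the disabling half of the next entry. No rule says which takes precedence, so the grades overlap.

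**Step 5. Find where the grades are used.** The only stated use is the RCP summary. Power Calculations and Statistical Analyses covers time to conversion by Cox and Kaplan-Meier methods, and then: "The secondary and tertiary outcome variables, all treated as continuous variables, will be examined as a function of treatment condition and site". Those outcomes are symptoms and functioning. No adverse-event analysis, tolerability endpoint or comparison of arms by grade appears there or elsewhere. The misclassification therefore reaches the RCP summary and any graded safety description written for aim 3.

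**The case against.** The strongest reply is that the wording is loose but little depends on it. Several parts of that reply stand.

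- **A lost comparison.** A reader might infer that a planned comparison of tolerability between arms loses its key category. The documents do not support this. They plan no comparison by grade and call no grade key. That aim 3 has no adverse-event analysis at all is a separate matter.
- **Illness course.** A reader might also infer that the upper grades would measure the course of the illness instead of tolerability, because a psychiatric admission is graded Severe automatically. The plan has a separate five-level attribution scale, from definite to unrelated. An admission for the underlying condition can be graded Severe and attributed as unlikely or unrelated. Grade alone mixes the two, but grade read with attribution does not.
- **Other records.** Side-effect queries, dose reductions or discontinuations, pill counts and treatment logs (Protections Against Risk, item 4; Table 1) would show that a participant took fewer capsules or stopped. They preserve some tolerability information. They do not grade the event that led to the change.
- **Is every upper-grade event serious?** Not strictly. The grade above Severe says only disabling, whereas the serious definition requires the disability to be lasting or significant. A briefly disabling event could be placed there without being serious. The three upper grades also rank serious events, which a yes/no flag would not do.
- **Seriousness is already defined separately.** This is true, and that definition, not the grade, governs the 24-hour reporting rule. Part of the remedy is therefore in place.

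None of this supplies an intensity grade for non-serious events or resolves the overlap on disability.

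**Conclusion.** The point holds as a classification defect of limited reach. It is a stated rule that puts events in the wrong category, not an omitted detail. An intense event that meets no listed outcome, and is not life-threatening, disabling or fatal, is graded moderate at most, and a disabling event can take either of two grades.

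The size can be given only in structure: two undefined grades for all non-serious events (apart from a briefly disabling one), and one overlap between adjacent upper grades. How many events would be misgraded is unknown. The documents give no rate of intense non-serious events, and the plan expects adverse events in general to be uncommon.

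The conclusion rests on two assumptions. Sites are taken to apply the list as written, with no intensity guide in a form or manual outside these documents. The expected gastrointestinal and taste effects are taken to be mostly non-serious.

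It does not extend to the trial's efficacy conclusions or to expedited reporting. It is still worth correcting because safety and tolerability are a stated aim, the graded summary informs a body that can halt the study, and the correction is cheap.

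**What to change.** 1. Define mild, moderate and severe by intensity or by interference with daily activity, with a short description of each.
2. Take the outcome criteria out of the Severe entry. Record seriousness as a separate yes/no item using the existing serious-event definition, unchanged.
3. Place disability in one grade only, so that the grades are mutually exclusive.
4. State that grade, seriousness and the existing attribution will be summarised together by randomised arm for aim 3. To protect the blind, arm-level tables would go to the DSMB or into the final report.

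The cost is a wording change to the grading list and possibly one field on the adverse-event form. The form is not among the documents, so it may already carry a seriousness item. Any events already graded would need re-review against the new definitions, preferably by someone blind to arm. No visits, participants, treatment rules, sample size, alpha or power change.
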